### **8.4 Warnings and precautions**

No evidence available at the time of the approval of this study protocol indicated that special warnings or precautions were appropriate, other than those noted in the provided Investigator Brochure. Additional safety information collected between IB updates will be communicated in the form of Investigator Notifications. This information will be included in the patient informed consent and should be discussed with the patient during the study as needed.

### **8.5 Data Monitoring Committee**

A data monitoring board will not be used for this study. This is an open-label, Phase I-II study in which all patients receive single-agent PDR001. Novartis will have access to the Safety Data on a regular basis. Novartis will host investigator teleconferences on a regular basis during the study. Further, during the phase I part of the study Novartis and the investigators will meet at the end of each treatment cohort to discuss and evaluate all of the gathered safety data. At the dose escalation teleconference the clinical course (safety information including both DLTs and all CTCAE Grade 2 or higher toxicity data during the first cycle of treatment, and PK data) for each patient in the current dose cohort will be described in detail. Updated safety data on other ongoing patients, including data in later cycles, will be discussed as well.

Dose escalation decisions will be based on a clinical synthesis of all relevant available data and not solely on DLT information. Selection of the actual dose for the next cohort of patients will be guided by the BLRM with EWOC, the Bayesian linear model describing the relationship between dose and PDR001 exposure, and a medical review of relevant clinical, PK and laboratory data. Novartis and the investigator parties must reach a consensus on whether to declare MTD, escalate the dose any further, or whether to de-escalate and/or recruit an additional cohort of patients at the current dose level ([Section 10.4.2](#) and [Section 10.7](#)).

During the phase II part of the study Individual patient data will be reviewed on an ongoing basis and aggregate safety data and the primary endpoint will be monitored quarterly by the

study team across the duration of the trial. The data review and analysis will be based on the available investigator reported data in the clinical database at that time ([Section 10.7](#)).

## **9 Data collection and management**

### **9.1 Data confidentiality**

Information about study subjects will be kept confidential and managed under the applicable laws and regulations. Those regulations require a signed subject authorization informing the subject of the following:

- What protected health information (PHI) will be collected from subjects in this study
- Who will have access to that information and why
- Who will use or disclose that information
- The rights of a research subject to revoke their authorization for use of their PHI.

In the event that a subject revokes authorization to collect or use PHI, the investigator, by regulation, retains the ability to use all information collected prior to the revocation of subject authorization. For subjects that have revoked authorization to collect or use PHI, attempts should be made to obtain permission to collect follow-up safety information (e.g. has the subject experienced any new or worsened AEs) at the end of their scheduled study period.

The data collection system for this study uses built-in security features to encrypt all data for transmission in both directions, preventing unauthorized access to confidential participant information. Access to the system will be controlled by a sequence of individually assigned user identification codes and passwords, made available only to authorized personnel who have completed prerequisite training.

Prior to entering key sensitive personally identifiable information (Subject Initials and exact Date of Birth), the system will prompt site to verify that this data is allowed to be collected. If the site indicates that country rules or ethics committee standards do not permit collection of these items, the system will not solicit Subject Initials. Year of birth will be solicited (in the place of exact date of birth) to establish that the subject satisfies protocol age requirements and to enable appropriate age-related normal ranges to be used in assessing laboratory test results.

### **9.2 Site monitoring**

Before study initiation, at a site initiation visit or at an investigator's meeting, Novartis personnel (or designated CRO) will review the protocol and CRFs with the investigators and their staff. During the study, the field monitor will visit the site regularly to check the completeness of patient records, the accuracy of entries on the CRFs, the adherence to the protocol to Good Clinical Practice, the progress of enrollment, and to ensure that study treatment is being stored, dispensed, and accounted for according to specifications. Key study personnel must be available to assist the field monitor during these visits.

The investigator must maintain source documents for each patient in the study, consisting of case and visit notes (hospital or clinic medical records) containing demographic and medical information, laboratory data, electrocardiograms, and the results of any other tests or assessments. All information recorded on CRFs must be traceable to source documents in the

patient's file. The investigator must also keep the original signed informed consent form (a signed copy is given to the patient).

The investigator must give the monitor access to all relevant source documents to confirm their consistency with the CRF entries. Novartis monitoring standards require full verification for the presence of informed consent, adherence to the inclusion/exclusion criteria and documentation of SAEs. Additional checks of the consistency of the source data with the CRFs are performed according to the study-specific monitoring plan.

### **9.3 Data collection**

For studies using Electronic Data Capture (EDC), the designated investigator staff will enter the data required by the protocol into the Electronic Case Report Forms (eCRF). The eCRFs have been built using fully validated secure web-enabled software that conforms to 21 CFR Part 11 requirements, Investigator site staff will not be given access to the EDC system until they have been trained. Automatic validation programs check for data discrepancies in the eCRFs and, allow modification or verification of the entered data by the investigator staff.

The Principal Investigator is responsible for assuring that the data entered into eCRF is complete, accurate, and that entry and updates are performed in a timely manner.

PK and biomarker (blood, serum, plasma and/or tissue) samples obtained during the course of the study will be collected from the Investigator sites and analyzed by a Novartis designated laboratory, contracted central laboratories, or local laboratories. ECG data collected during the study until the CSR cut-off date is reached will be reviewed and processed centrally by a specialist CRO. During the course of the study, Novartis may decide to have a central review of the radiological assessments performed. In such case, the investigator's staff will be instructed on how to send data from these radiological assessments to a Contract Research Organization (CRO) for central review when needed. Designated investigational site staff will enter the information required by the protocol into the appropriate eCRF and/or designated laboratory requisition forms. Field monitors will review the eCRFs and laboratory paper requisition forms for accuracy and completeness and instruct site personnel to make any required corrections or additions. One copy of the requisition form will be forwarded to each analytical laboratory with the respective sample(s) by the field monitor or by the designated investigational site staff; and one copy will be retained at the investigational site.

### **9.4 Database management and quality control**

For studies using eCRFs, Novartis personnel (or designated CRO) will review the data entered by investigational staff for completeness and accuracy. Electronic data queries stating the nature of the problem and requesting clarification will be created for discrepancies and missing values and sent to the investigational site via the EDC system. Designated investigator site staff are required to respond promptly to queries and to make any necessary changes to the data.

Concomitant treatments and prior medications entered into the database will be coded using the WHO Drug Reference List, which employs the Anatomical Therapeutic Chemical classification system. Medical history/current medical conditions and adverse events will be coded using the Medical dictionary for regulatory activities (MedDRA) terminology.

Samples and/or data will be processed centrally and the results will be sent electronically to Novartis (or a designated CRO).

For EDC studies, after database lock, the investigator will receive a CD-ROM or paper copies of the patient data for archiving at the investigational site.

## 10 Statistical methods and data analysis

It is planned that the data from participating centers in this protocol will be combined, so that an adequate number of patients will be available for analysis.

Study data will be summarized with respect to demographic and baseline characteristics, efficacy observations and measurements, safety observations and measurements, and all relevant PK and PD measurements.

Categorical data will be presented as contingency tables (frequencies and percentages). For continuous data summary statistics of mean, standard deviation, median, minimum, and maximum will be presented.

The primary clinical reporting of the dose escalation, and each of the Phase II indications will take place when all patients in the escalation, or relevant indication have discontinued, or completed at least six cycles of treatment. This time can be indication specific, therefore a single primary CSR, or several primary CSRs may be prepared which may include more than one indication. Additional data from patients continuing treatment after the data cutoff for the corresponding primary CSR will be reported in a final CSR once all patients have completed study ([Section 4.3](#)).

The following rules will be followed for reporting results unless stated otherwise:

- For the phase I, cohorts treated with the same dose level and schedule of PDR001 will be pooled into a single treatment group. All summaries, listings, figures and analyses will be performed by treatment group.
- For the phase II, all summaries, listings, figures and analyses will be performed by disease group and treatment regimen. Patients from the expansion phase will be classified according to the group to which they were assigned at baseline based on the disease type and regimen. The different groups are:
  - Group 1a: NSCLC, RP2D regimen
  - Group 1b: NSCLC, 300 mg Q3W regimen
  - Group 2: Melanoma, RP2D regimen
  - Group 3: Triple negative breast cancer, RP2D regimen
  - Group 4: Anaplastic thyroid cancer, RP2D regimen

Note: patients from the dose escalation and the expansion will not be pooled in any analyses unless otherwise specified.

Screen failure patients are those who signed the informed consent, but never started the study treatment for any reason. For these patients, the eCRF data collected will not be included in analyses, but will be reported in the clinical study report (CSR) as separate listings.

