#### Phase II part

Once the MTD and/or RP2D have been declared, additional patients will be enrolled in the Phase II part in order to assess the preliminary anti-tumor activity of PDR001.

In the phase II part, patients will be assigned to different groups depending on the tumor type and dosing regimen as shown in [Figure 4-1](#). Please refer to [Section 5.1](#) for further details.

Groups 1a, 1b and 2 will enroll approximately 60 patients each, group 3 will enroll approximately 40 patients, and group 4 will enroll approximately 10 patients. Enrollment to any of these groups may be stopped with fewer patients if achieving these enrollment targets is not logistically feasible. The relatively small size of the anaplastic thyroid cancer group reflects the low prevalence of anaplastic thyroid cancer; this group may be increased in size to

[figure not shown]
approximately 40 patients based on feasibility of enrollment and if PDR001 appears to be active (at least one response or other efficacy data show preliminary anti-tumor activity in the first 10 patients) in this disease. A Bayesian design will be used in order to estimate ORR within each group. Details of the sample size calculations leading to the patient numbers are provided in [Section 10.8](#).

After a preliminary assessment of the safety profile in the phase I part, a decision may be made to test up to two regimens of PDR001 during the phase II part to better assess the efficacy, safety and benefit-risk of PDR001. If a second regimen is to be studied, then this would be done in one or more disease indications chosen based in part on logistical feasibility. The two regimens would be assigned in an alternating fashion to patients of the same disease group across all the sites in this global study. The number of patients tested at this second regimen will be similar to the number of patients to be enrolled in this disease setting at the RP2D.

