### 7.1.3 Treatment period

A treatment cycle is defined as 28 days for the Q2W and Q4W regimens and 21 days for the Q3W regimen, for the purposes of scheduling procedures and evaluations. Please refer to Table 7-1 for details of the timing of required assessments and Section 7.1 for visit windows.

Patients will be treated until they experience unacceptable toxicity, progressive disease per irRC and/or treatment is discontinued at the discretion of the investigator or the patient, as described in Section 7.1.4 and Section 4.3. Patients should not discontinue treatment based on progressive disease per RECIST.

Patients who have disease progression and have evidence of clinical benefit, such as disease shrinkage at other sites or symptomatic improvement, may continue treatment with PDR001. In addition, PDR001 treatment may be temporarily interrupted to permit local therapy for symptomatic metastases after disease progression has been documented. Patients who continue on treatment after disease progression should discontinue study treatment once they are no longer deriving benefit as assessed by the investigator.

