## **7.2 Assessment types**

### **7.2.1 Efficacy assessments**

Tumor response will be determined locally according to two sets of criteria:

1. RECIST v1.1 ([Appendix 1](#))
2. irRC ([Appendix 2](#))

The local investigator's assessment will be used for the analysis of response according to both RECIST 1.1 and irRC, and for treatment decision making (study discontinuation due to PD as per irRC). During the course of the study, Novartis may decide to have a central review of the radiological assessments performed. In such case, the investigator's staff will be instructed on how to send data from these radiological assessments to a Contract Research Organization (CRO) for central review when needed.

At screening, all patients will undergo CT with i.v. contrast of the chest, abdomen and pelvis. If there is clinical evidence of disease in the neck, a CT with i.v. contrast of the neck will also be performed. MRI should only be used to evaluate sites of disease that are not adequately imaged by CT. If a patient is intolerant of iodine-based contrast agents, CTs may be performed without contrast. MRI may be used to evaluate sites of disease where a CT without i.v. contrast is not adequate. Visible skin lesions and easily palpable subcutaneous tumors may be measured

by physical examination using a ruler or calipers. Ultrasound should not be used to measure sites of disease. See [Table 7-2](#) for further details.

Tumor assessments will be performed at the following time points:

- Screening
- Every 8 weeks  $\pm$  1 week from 8 weeks post Cycle 1 Day 1 up to 40 weeks, then every 12 weeks  $\pm$  1 week until progression of disease per irRC or patient withdrawal. After EOT, during disease progression f/u, every 8 weeks  $\pm$  1 week until 40 weeks, then every 12 weeks  $\pm$  1 week until progression of disease per irRC, withdrawal of consent or lost to follow-up.
- PR or CR, per both RECIST 1.1 and irRC, will be confirmed by a new assessment after at least 4 weeks. Also PD, as per irRC, will be confirmed after at least 4 weeks.
- At the End of Treatment, if a scan was not conducted within 30 days prior to End of Treatment

Disease progression follow-up should be performed as described in [Section 7.1.6](#).

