## Phase II

A Bayesian design will be used in order to estimate ORR within each group (Group 1a: NSCLC treated at the RP2D regimen (i.e. Q4W), Group 1b: NSCLC treated at a Q3W regimen, Group 2: melanoma, Group 3: TNBC, Group 4: anaplastic thyroid cancer), and it will be used to provide inferential summaries (e.g., mean, median, interval probabilities) in relation to the patient population for each of the disease groups (defined in [Section 5.2](#)). Sample size for each

treatment group is provided in [Section 4.1](#) and details of the sample size calculations in [Section 10.8](#).

For a Bayesian design, a prior distribution for the parameter of interest, ORR, must be specified. For the current study, the prior clinical assumption for PDR001 in the selected patient populations is used in order to derive a minimally informative unimodal Beta prior distribution that reflects the level of uncertainty around ORR before starting the current trial ([Neuenschwander et al 2008](#)). The prior mean ORR is set to be equal to 20% and the parameters of the minimally informative Beta prior distribution of ORR have been set up as follows:

- $a/(a+b) = 0.2$
- $a = 0.25$
- $b = 1.0$

At primary analysis, this prior distribution will be updated with all the data available from the patients in the FAS. See sample size estimation in [Section 10.8](#).

**Groups 1a, 1b and 2 (NSCLC and melanoma):** Estimates of the ORR for each group along with mean, median, standard deviation, and 95% credible intervals and the interval probabilities for the true ORR lying within [0%, 15%), [15%, 20%), [20%, 30%), [30%, 50%) and [50%, 100%] will be presented.

If the observed ORR is equal to or greater than 20% (i.e.  $\geq 12$  responses (CR or PR) out of 60 patients) for NSCLC and 30% (i.e.  $\geq 18$  responses (CR or PR) out of 60 patients) for melanoma, then this will be considered as preliminary evidence of activity of PDR001 in the respective Groups.

Note that for a sample size of  $n = 60$ ,

- for NSCLC (group 1a or 1b), if the observed ORR is 20% then the posterior probability of true ORR greater than 15% is 83.7%.
- for melanoma, if the observed ORR is 30% then the posterior probability of true ORR greater than 20% is 96.2%.

**Group 3 (TNBC):** Estimates of the ORR along with mean, median, standard deviation, and 95% credible intervals and the interval probabilities for the true ORR lying within the intervals stated below will be presented.

- [0, 10%) unacceptable efficacy

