1.3.1 Data included in the analyses

Analyses for the dose-escalation part will be based on all patients' data up to the time when all patients have either completed at least one cycle of treatment or have discontinued due to DLTs. To determine the MTD, only DLTs that occur during Cycle 1 and patients belonging to the Dose-determining safety set (DDS) ([CPDR001X2101 Amendment 8 Section 2.3.4]) will be considered for inclusion into the Bayesian models in the dose-escalation part.

Dose-escalation meetings

At each dose-escalation meeting results from the adaptive Bayesian linear model for dose-exposure and the adaptive BLRM for DLT analysis will be provided. In order to provide a timely response, these results are based upon information provided by the clinical team, rather than data held in the clinical database.

Primary CSR

SAP final CSR 24-Jul-2020 (11:48)

The primary clinical reporting of the dose escalation, and each of the Phase II indications will take place when all patients in the escalation, or relevant indication have discontinued, or completed at least six cycles of treatment. This time can be indication specific, therefore a single primary CSR, or several primary CSRs may be prepared which may include more than one indication.

Final CSR

Any additional data for patients continuing on study past the data cut-off for the corresponding primary CSR, as allowed by the protocol, will be summarized in a subsequent final CSR.

2 Definitions and general methodology

2.1 **General definitions**

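### The Phase II primary cut-off counts cycles, so it guarantees 24 weeks of follow-up on Q4W but only 18 on Q3W; late-starting Group 1b patients may be unable to confirm a week-16 response in time

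*Protocol*

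**What the plan says.** Protocol section 10 sets the time of primary reporting for each Phase II indication as "when all patients in the escalation, or relevant indication have discontinued, or completed at least six cycles of treatment". SAP section 1.3.1 repeats the condition ("completed at least six cycles of treatment"). The unit is the indication: "This time can be indication specific, therefore a single primary CSR, or several primary CSRs may be prepared which may include more than one indication".

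Cycle length depends on the regimen (protocol section 7.1.3): "A treatment cycle is defined as 28 days for the Q2W and Q4W regimens and 21 days for the Q3W regimen". Group 1a receives the Q4W regimen (section 10.4.2). The other NSCLC group is "Group 1b: NSCLC, 300 mg Q3W regimen". Where two regimens are tested in one disease, section 4.1 says: "The two regimens would be assigned in an alternating fashion to patients of the same disease group".

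Tumour assessment does not depend on the regimen. Section 7.2.1 and Table 7-1 schedule scans every 8 weeks, within 1 week either way, up to week 40. Section 7.2.1 adds: "PR or CR, per both RECIST 1.1 and irRC, will be confirmed by a new assessment after at least 4 weeks". Appendix 1 (section 14.1.3.1) requires confirmation in a non-randomized trial with response as its primary endpoint.

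Section 10.4.2 estimates the primary ORR from the FAS data available at the primary analysis and treats 12 or more responses in 60 as preliminary evidence of activity in each NSCLC group. Neither document states a minimum follow-up in weeks or a rule to wait for pending confirmations. The data-analysis entry of the protocol summary words the cut-off differently, in terms of all patients in both parts of the study.

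**The concern.** The cut-off runs on cycles, while the endpoint runs on the calendar. The follow-up guaranteed before the primary ORR is calculated therefore depends on the regimen, and the shorter guarantee falls on Group 1b. A partial response still unconfirmed at the cut-off is not a response in the primary analysis, so truncation can lower the confirmed ORR for a reason unrelated to the drug or its schedule.

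This matters because the Amendment 04 rationale says that Group 1b was added to support the choice of dose and regimen. Groups 1a and 1b are likely to be read side by side, and each is held against the same 12/60 rule. SAP section 3.4 itself recognises that response to immunotherapy may come late.

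**Working it through.** **The plan's own figure.** With X ~ Binomial(60, 0.20), P(X ≥ 12) = 55.1%, which agrees with Table 10-2.

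**Guaranteed follow-up, ignoring dose delays.**
- Q4W: 6 × 28 / 7 = 24 weeks.
- Q3W: 6 × 21 / 7 = 18 weeks.

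**Earliest confirmation.**
- First response at week 8: week 12 at the earliest, with the next scheduled scan at week 16. Both fall within 18 weeks.
- First response at week 16: 16 + 4 = week 20 at the earliest (week 19 if scanned at week 15, week 21 if at week 17), with the next scheduled scan at week 24. All fall after 18 weeks.

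**Effect of the indication-level trigger.** Let g be the weeks between the first dose of the last Group 1a patient who reaches six cycles and the first dose of a later Group 1b patient. The NSCLC cut-off waits for both, so the 1b patient has at least max(24 - g, 18) weeks.

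| g (weeks) | Minimum 1b follow-up (weeks) | Week-20 confirmation possible | Scheduled week-24 scan reached |
|---|---|---|---|
| 0 | 24 | yes | yes |
| 1 | 23 | yes | no |
| 4 | 20 | yes | no |
| 5 | 19 | no | no |
| 6 or more | 18 | no | no |

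At nominal scan times, a week-16 response is at risk if g > 4, or if g > 0 when the site confirms only at the scheduled week-24 scan.

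**Is g above 0 plausible?** The Amendment 05 status gives 5 NSCLC patients at 27-Mar-2016, before Amendment 04 (13-May-2016) created Group 1b. The Amendment 06 status gives 114 at 29-Jun-2017. That is 109 patients in 459 days (65.6 weeks), or 1.66 per week. With alternating assignment and equal targets, a 1a head start of k patients leaves about k trailing 1b patients, who take k / 1.66 weeks to enrol:
- k = 5: 3.0 weeks.
- k = 7: 4.2 weeks.
- k = 10: 6.0 weeks.

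Only k = 5 rests on a documented count. Amendment 04 needed ethics approval before implementation, so 1a could have gone on recruiting alone for a time; k = 7 and k = 10 are assumptions. The constant accrual rate is also an assumption.

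**Effect on the 12/60 rule.** Suppose m Group 1b patients are affected and a share f of responses is first seen at week 16 and lost. Then X = Bin(60 - m, p) + Bin(m, p(1 - f)). Neither m nor f is in the documents. At p = 0.20, against 55.1% with no loss:

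| m | f = 20% | f = 30% | f = 50% |
|---|---|---|---|
| 5 | 52.6% | 51.3% | 48.7% |
| 10 | 50.0% | 47.3% | 42.0% |

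The expected number of responses lost is m × 0.20 × f: 0.2 to 0.5 for m = 5, and 0.4 to 1.0 for m = 10.

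**The case against.** A reader might infer that late Group 1b patients cannot confirm a week-16 response. The documents do not support that. The trigger is per indication and the regimens were to be assigned alternately; if the two groups close together, 1b patients have about 24 weeks. At the documented accrual rate, the five-patient head start gives a gap of only about 3 weeks, leaving the last 1b patient about 21 weeks, enough for a week-20 scan. Section 7.2.1 lists confirmation as an item of its own, so a week-20 scan is provided for, although Table 7-1 shows no separate confirmatory visit.

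A reader might also put the cost at a fall from 55.1% to 42.4%. The second figure is P(X ≥ 13) and assumes that exactly one response is lost with certainty. With five affected patients at a true ORR of 20%, only one responder is expected among them (5 × 0.20), and not every response will first appear at week 16.

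Further points stand. Eighteen weeks is a floor: the rule says at least six cycles, and delays lengthen cycles. No formal comparison of 1a with 1b is planned. Truncation also affects Q4W, since a response first seen at week 24 cannot be confirmed by week 24. Later data go to the final CSR, and the SAP's best-response rule would pick up late confirmations there.

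These points limit the effect without removing the defect. The final CSR does not repair the primary ORR, which is judged against 12/60 at the primary cut-off. Discontinued patients satisfy the trigger at once, so g runs from the last 1a patient still treated at six cycles and can exceed the enrolment gap.

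**Conclusion.** The point holds as a conditional weakness. The stated rule guarantees 6 weeks less follow-up on Q3W than on Q4W (24 - 18), and the Q3W guarantee is too short to confirm a week-16 response. Whether that happens depends on g: more than 4 weeks if a confirmatory scan is done at week 20, any positive value if it waits for week 24. The documents do not show that any patient was affected. They give no enrolment dates by NSCLC group, and the effect may be nil.

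Under the assumptions shown, the loss in the chance of meeting the 12/60 rule at a true ORR of 20% is about 2.5 to 6.4 percentage points with 5 affected patients (55.1 - 52.6; 55.1 - 48.7) and 5.1 to 13.1 points with 10 (55.1 - 50.0; 55.1 - 42.0). This is a cheap improvement, of minor to moderate severity.

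**What to change.** In protocol section 10 and SAP section 1.3.1, define the Phase II primary cut-off in calendar time, identically for Groups 1a and 1b. Every treated patient should have at least 24 weeks from first dose, with the week-24 scan (allowing its 1-week window) and any pending confirmatory scan done, or should have ended tumour assessment. Bring the data-analysis entry of the protocol summary into line with that rule.

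The change is to wording only. Its downside is time. If a Group 1b patient is last, the NSCLC cut-off may move about 6 weeks later, or more if a confirmatory scan is pending: a response first seen at week 24 cannot be confirmed before week 28.

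If the NSCLC primary cut-off has already passed, the same rule can be applied to both groups in the final CSR, with a count by group of responses that were unconfirmed at the primary cut-off and confirmed later.
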